4. STUDY DESIGN

4.1. Overall Study Design

The purpose of this Phase I randomized, double-blind clinical trial is to optimize ALFQ dosing. Safety will be assessed through the frequency of the overall and specific post-vaccination reactions. Blood will be collected to assess humoral, cell-mediated, and innate immune responses.

Healthy adults not living with HIV who are available for 14 months will be enrolled. A total of 60 participants will be enrolled to one of three arms, each comprised of 20 candidate vaccine recipients. Each arm will receive identical doses of A244 and B.63521 (300 micrograms of each). In addition, Arm 1 will receive 200 micrograms of ALFQ. Arm 2 will receive 100 micrograms of ALFQ. Arm 3 will receive 50 micrograms of ALFQ. The safety, reactogenicity, and immunogenicity will then be compared among the three arms to determine the optimal dose of ALFQ.

All vaccinations will be split into 2 half doses which will both be administered intramuscularly (IM) into the same deltoid muscle. Vaccinations will occur at months 0, 1, and 2. The second vaccination will be administered into the contralateral deltoid at study month 1 compared to the first vaccination at study month 0. The third vaccination at study month 2 will be administered into the same deltoid as the first vaccination at study month 0. Participants will be followed for 12 months following the last study vaccination. Safety and tolerability will be assessed with both clinical and laboratory monitoring. Vaccine- related reactions will be observed and solicited for 30 minutes post-vaccination and with the aid of a diary card and interview of participants during the 14 days post vaccination.

The information gained from the review of the diary card and the interview with the participants will be documented in the clinical study chart. In addition, AEs will be documented at each clinical encounter. AEs will be graded for seriousness, severity, and relationship to the investigational product.

4.2. Number of Participants

The site will screen approximately 150 participants to achieve a total of 60 enrolled.

4.3. Sentinel Group Allocation

A sentinel group including 6 participants will be enrolled. Four participants in the sentinel group will be randomized to the 200 mcg ALFQ group (Arm 1), one participant will be randomized to the 100 mcg ALFQ group (Arm 2), and one participant will be randomized to the 50 mcg ALFQ group (Arm 3). Safety data for seven days following vaccination one will be reviewed by a PSRT. If it is determined to be necessary by the PSRT, the MHRP SMC will be consulted to review unblinded data to provide a recommendation on continuing enrollment. Additionally, the PSRT will consult the SMC if either of the following conditions are met:

- 1) One (or more) participants experience an SAE that is assessed as related to a study agent, or
- 2) Two (or more) participants experience grade 3 or 4 AEs of the same type (e.g., elevated ALT) related to a study agent. This would exclude monitoring lab values if a clear alternate etiology is identified. Additionally, CBC differential counts would not contribute.

After safety has been confirmed by PSRT review, the remaining 54 participants will be enrolled.

4.4. Scientific Rational for Study Design

To date there have been no comparative studies regarding optimal dosing of adjuvant ALFQ. The ALFQ doses in Arm 1, 2, and 3 are based on the MPLA/(3D-PHAD®) component of ALFQ. ALFQ has been demonstrated to elicit potent antibody binding responses in animal models.

ALFQ adjuvant dose optimization has the potential to limit AEs and improve efficiency and cost effectiveness of vaccine administration while maximizing immunogenicity. As a result, RV575 will perform a dose de-escalation study.

4.5. Justification for Dose

The A244 protein was included in the AIDSVAX vaccine at the 300 microgram dose. This dose was found to be safe and well tolerated.²⁴

B.63521 has been tested in animal trials at doses up to 300 micrograms. It has not yet been utilized in human trials. B.63521 is very similar to the MN protein utilized in AIDSVAX which was administered at the 300 microgram dose in RV 144.¹⁰

ALFQ had already demonstrated safety and immunogenicity at the 200 microgram and 100 microgram dose. (Hutter, ASTMH, 2020)

This study will contribute information about safety and immunogenicity of ALFQ at the 50 microgram dose and perform a direct dose comparison for both safety and immunogenicity. This data is essential to optimizing efficiency of adjuvant inclusion in future vaccine trials.

4.6. Method of Treatment Assignment

Randomization will be conducted using a randomization block scheme described in a separate randomization plan held by the protocol statistician. The randomization list will be generated by the protocol statistician and provided and trained on with the site delegated un-blinded study staff/nurse. Once a randomization number has been assigned, it will not be re-assigned.

4.7. End of Study Definition

The end of the study primary completion date is defined as the last subject last visit (LSLV). Each participant will be followed for 12 months after the final vaccination. Follow up includes 10 months of clinic visits and two additional telephone follow up visits at 1-month intervals for a total of 12 months. The completion of laboratory assays and data analysis is anticipated to take up to 5 years from the primary completion date.

5. STUDY POPULATION

5.1. Participant Recruitment

The study population will consist of 60 healthy adults not living with HIV between the ages of 18 and 55 years at the time of study enrollment at the WRAIR CTC.

Healthy adult volunteers, male and female, will be recruited by noncoercive means through the WRAIR CTC according to applicable US Army regulations. Participants will be recruited from the Baltimore-Washington, D.C. metro area through the WRAIR CTC according to applicable U.S. Army regulations (i.e., 32 CFR 219 and 21 CFR 50, 54, 56, and 312). Adult men and women will be recruited by the use of WRAIR IRB approved advertisements using multiple media formats, to include, but not limited to: newspapers, flyers, emails, the WRAIR CTC website, postings on public listservs, social media (such as Facebook or other apps/websites), posters, bus ads, generic radio and television ads, word of mouth and referrals from volunteers currently in studies. Email announcements will include information on ad posters excluding any photos unless attached as complete flyer. See [Appendix F](#) below for the recruitment script. Recruitment may also include oral presentations (using standardized audio script) at events and

meetings. All advertisements, both general and specific to this study, will have been reviewed and approved by the WRAIR IRB prior to their use. All recruiting methods will direct the volunteer to contact the CTC via e-mail or phone, or to the CTC web site where the same contact information will be given.

In the case of oral presentations and other meeting-related recruitment, potential subjects may be given the opportunity to sign up directly for a briefing and screening appointment. Any subject who so desires will be asked to provide basic contact information and an appointment made.

Upon calling the recruitment phone number, a recruitment script will be used by study personnel to inform potential subjects of the details of the study. If the potential subject desires, some basic contact information will be obtained and an appointment for a formal briefing and screening will be made at that time.

Upon contacting the CTC via e-mail, potential participants will be provided an electronic version of the recruitment script to inform them of the details of the study. If the potential subject desires, some basic contact information will be obtained and an appointment for a formal briefing and screening will then be made (via further e-mail or phone conversations).

Given the value of the information in this recruitment script, a version of the script without compensation figures will be submitted as a separate “information flier” to be used on the WRAIR CTC web site, email correspondence (as noted above), and other electronic or social networking platforms.

Participants who have participated in studies at the WRAIR CTC will be given the opportunity to receive compensation for referring additional subjects. Subjects will be asked to direct interested persons to contact the CTC. Subjects will receive \$50 for each referred person who then attends a screening session and meets all inclusion and none of the exclusion criteria.

Compensation will be independent of the referred person’s decision to enroll. Final authority over dispensation of referral compensation will lie with the CTC Director.

Volunteers can also be recruited via WRAIR 2038, which is a generic screening protocol managed by the WRAIR CTC. Under this screening protocol, volunteers will undergo a generic screening visit with medical history, exam, vitals, lab tests, along with other potential screening tests. If the volunteer is interested in learning about this clinical trial, they will need to attend a briefing and sign this study’s informed consent form. If the volunteer consents, the screening documentation from WRAIR 2038 can be shared with this study to fulfill screening requirements, and a copy of said documents can be added to the volunteer’s study file for this clinical trial.

5.2. Participant Identification Numbers

All participants consented will be assigned a Participant Identification Number (PIN), which is a 7-digit number. The first three digits are the protocol number (575), followed by a 4-digit number which, will be assigned sequentially.

The PIN will be used to label all source documents, Case Report Forms (CRFs) and specimens. Source documents, CRFs and specimens are never labeled with participant names or national identification numbers.

5.3. Participant Eligibility

Screening for eligible participants will be performed within 45 days prior to administration of the investigational vaccine. Participants who have passed the TOU and have given written informed consent will undergo a complete medical history, physical examination, and screening laboratory assessments to determine eligibility for study participation. Screening assessments (found in the SOE) will be completed after the informed consent process has been completed.

Screening evaluations for specific eligibility criteria (see [Section 5.3.1](#) and [Section 5.3.2](#)) must be completed within the screening visit window specified ([Table 1](#)) prior to enrollment.

Counseling for HIV risk reduction and the potential risks of becoming pregnant during participation will be provided. The PI or designee will make the final decision regarding eligibility. Clinical data and specimens collected during screening from participants subsequently found to be ineligible for participation in the study will become part of the study records and specimens will be evaluated in accordance with protocol procedures. One re-screening attempt will be allowed if the there was an elevation and laboratory values on the first screening attempt which is suspected to be temporary, and or insignificant by the study personnel. Only eligible participants will be given the investigational product at the enrollment visit. A participant is considered enrolled in the study upon receipt of the first study vaccination.

5.3.1. Inclusion Criteria

Potential participants are required to meet all of the following criteria for enrollment into the study.

1. Healthy adults between the ages 18-55 years (inclusive)
2. Must be at low risk for HIV infection per investigator assessment and using the study risk assessment tool.
3. Able and willing to provide written, informed consent
4. Able and willing to comply with all research requirements, in the opinion of the Investigator
5. Agreement to refrain from blood donation during the course of the study and within the 2 months prior to study entry
6. Minimum body weight of 110 pounds (lbs) (50kg)
7. Laboratory Criteria within 45 days before enrollment:
 - a. Hemoglobin $\geq 11.7\text{g/dL}$ for women; $\geq 12.5\text{ g/dL}$ for men
 - b. White Blood Cell count = $3,500\text{-}10,800\text{ cells/mm}^3$
 - c. Platelets $\geq 140,000/\text{mm}^3$ and $\leq 450,000/\text{mm}^3$
 - d. Alanine aminotransferase (ALT; SGPT) $< 1.25 \times \text{ULN}$
 - e. Serum creatinine $\leq 1.25 \times \text{institutional upper limit of the reference range}$

- f. Negative HIV testing (HIV Ab / antigen 4th generation screen with reflex confirmatory RNA testing)
- g. Negative HBsAg and hepatitis C antibody testing

Note: As above, Grade 1 lab abnormalities detected on screening may be repeated at PI discretion. Persistent Grade 1 abnormalities that are felt to represent the non-pathologic baseline for the subject will be documented before a subject is enrolled in the trial and are allowable per discretion of the PI.

8. Birth control requirements:

All participants assigned female at birth must meet one of the following 2 criteria:

- a. No reproductive potential due to post-menopausal status (12 months of natural [spontaneous] amenorrhea) or hysterectomy, bilateral oophorectomy, or tubal ligation
- b. People of childbearing potential should agree to practice highly effective contraception at least 30 days before enrollment and through 3 months post-last vaccination, using one of the following methods: condoms (male or female) with spermicide; diaphragm, or cervical cap with spermicide; intrauterine device; contraceptive pills, patch, injection, intravaginal ring or other FDA-approved contraceptive method; male partner has previously undergone a vasectomy; abstinence
- c. All participants are encouraged to engage in safe sex practices to prevent HIV acquisition

9. For all participants assigned female at birth, except those with a history of hysterectomy or bilateral oophorectomy, a negative β -HCG pregnancy test (urine) on the day of enrollment and each vaccination day is required. Because tubal ligations have a failure rate that is not insignificant, and 12 months of spontaneous amenorrhea can be a result of polycystic ovarian syndrome which does not completely preclude pregnancy, a negative β -HCG pregnancy test at enrollment and on each vaccination day is also required for all participants assigned female at birth with a history of either of these.

10. No plans to travel outside the Washington DC metro area (DC, Maryland, and Virginia) that would prevent compliance with planned study visits

11. Test of Understanding (TOU) (minimum passing score of 80% with 2 attempts permitted)

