
Inclusion Criteria
 
Potential participants are required to meet all of the following criteria for enrollment into the study.
 
1. Healthy adults between the ages 18-55 years (inclusive)2. Must be at low risk for HIV infection per investigator assessment and using the study risk assessment tool.3. Able and willing to provide written, informed consent4. Able and willing to comply with all research requirements, in the opinion of the Investigator5. Agreement to refrain from blood donation during the course of the study and within the 2 months prior to study entry6. Minimum body weight of 110 pounds (lbs) (50kg)7. Laboratory Criteria within 45 days before enrollment:
a. Hemoglobin \geq 11.7 g/dL for women; \geq 12.5 g/dL for menb. White Blood Cell count = 3,500-10,800 cells/mm³c. Platelets \geq 140,000/mm³ and \leq 450,000/mm³d. Alanine aminotransferase (ALT; SGPT) $<$ 1.25 x ULNe. Serum creatinine \leq 1.25 x institutional upper limit of the reference rangef. Negative HIV testing (HIV Ab / antigen 4th generation screen with reflex confirmatory RNA testing)g. Negative HBsAg and hepatitis C antibody testing8. Birth control requirements: 
Note: As above, Grade 1 lab abnormalities detected on screening may be repeated at PI discretion. Persistent Grade 1 abnormalities that are felt to represent the non-pathologic baseline for the subject will be documented before a subject is enrolled in the trial and are allowable per discretion of the PI.
 
All participants assigned female at birth must meet one of the following two criteria:
 
a. No reproductive potential due to post-menopausal status (12 months of natural [spontaneous] amenorrhea) or hysterectomy, bilateral oophorectomy, or tubal ligationb. People of childbearing potential should agree to practice highly effective contraception at least 30 days before enrollment and through 3 months post-last vaccination, using one of the following methods: condoms (male or female) with spermicide; diaphragm, or cervical cap with spermicide; intrauterine device; contraceptive pills, patch, injection,

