2.4.5. Unknown Risks

As with all research, there is the remote possibility of risks that are unknown or that cannot be foreseen based on current information. This would include late-onset effects.

Risks to unborn babies are unknown at this time; the effect of the candidate HIV vaccines on pregnancy and fetus are unknown as they have not been specifically studied in pregnant people. Participants who are pregnant or plan to become pregnant during the first 3 months post-vaccination will be excluded from enrollment. Female participants must use an adequate form of birth control including condoms (male or female) with spermicide, diaphragm, or cervical cap with spermicide, intrauterine device, contraceptive pills, patch, injection, intravaginal ring or other FDA-approved contraceptive method, male partner has previously undergone a vasectomy, or abstinence for 30 days prior to study injection until at least 3 months after receipt of the final study injection. A pregnancy test will be performed at screening, prior to the study injection (same day), and prior to any of the invasive procedures. Should a participant become pregnant within the 3 months post-study injection, she will be followed for safety to term. Partners of male participants who become pregnant will not be followed.

All participants are encouraged to engage in safe sex practices to prevent HIV acquisition.

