5.4.1. Contraception and Pregnancy

Risks to unborn babies and nursing infants are unknown at this time. Therefore, participants childbearing potential must agree to follow contraceptive guidance and must agree not to breastfeed while in the study and for 2 months after the study.

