5.4.1.1. Individuals of Childbearing Potential

Participants are not considered of childbearing potential if they meet any of the following criteria:

- Premenopausal with 1 of the following:
 - Documented hysterectomy

- Documented bilateral salpingectomy
- Documented bilateral oophorectomy
- Premenarchal
- Postmenopausal
- Defined as no menses for 12 months without an alternative medical cause (A high follicle stimulating hormone (FSH) level in the postmenopausal range may be used to confirm a postmenopausal state in women not using hormonal contraception or hormonal replacement therapy (HRT). However, in the absence of 12 months of amenorrhea, a single FSH measurement is insufficient.)
- People assigned female sex at birth on HRT and whose menopausal status is in doubt will be required to use one of the nonhormonal highly effective contraception methods if they wish to continue their HRT during the study, or they must discontinue HRT to allow confirmation of postmenopausal status before protocol enrollment

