5.4.1.2. Participants of Childbearing Potential

Participants of reproductive potential are eligible to participate if they agree to use a highly effective method of contraception as described the section below.

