5.4.1.3. Effective Methods of Contraception

Highly effective contraceptive methods that have a failure rate of <1% per year when used consistently and correctly:

- User Dependent Methods:
 - Oral, intravaginal, or transdermal combined (estrogen- and progestogen- containing) hormonal contraception associated with inhibition of ovulation
 - Oral or injectable progestogen-only hormonal contraception associated with inhibition of ovulation
- User Independent Methods:
 - Implantable progestogen-only hormonal contraception associated with inhibition of ovulation
 - Intrauterine device (IUD)
 - Intrauterine hormone-releasing system (IUS)
 - Bilateral tubal occlusion

- Vasectomized partner
- Sexual abstinence

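### Inclusion criterion 8b accepts a barrier method with spermicide as highly effective contraception, but the list to which Section 5.4.1.2 ties eligibility contains no barrier method

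*Protocol*

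**What the plan says.** The synopsis and Section 5.3.1 carry the same criterion 8b: "People of childbearing potential should agree to practice highly effective contraception at least 30 days before enrollment and through 3 months post-last vaccination". It continues "using one of the following methods: condoms (male or female) with spermicide; diaphragm, or cervical cap with spermicide", and then names the intrauterine device, pill, patch, injection, vaginal ring, any other FDA-approved method, a vasectomised partner and abstinence. One method is enough.

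Section 5.4.1 adds that "participants childbearing potential must agree to follow contraceptive guidance". Section 5.4.1.2 turns that guidance into an eligibility rule: "Participants of reproductive potential are eligible to participate if they agree to use a highly effective method of contraception as described the section below". The section below is 5.4.1.3, whose list opens "Highly effective contraceptive methods that have a failure rate of <1% per year when used consistently and correctly".

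Section 2.4.5 gives the barrier methods again under a weaker label: "Female participants must use an adequate form of birth control including condoms (male or female) with spermicide". On who decides, Section 5.3 says "The PI or designee will make the final decision regarding eligibility".

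**The concern.** The protocol uses one term, highly effective, with two different method lists, and both lists bear on who may be dosed. Site staff who screen from the inclusion criteria will accept a volunteer using only a condom, diaphragm or cervical cap with spermicide. Staff who apply Section 5.4.1.2 will not.

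The requirement protects against fetal exposure. Section 2.4.5 says that the risks to unborn babies are unknown. Sections 2.2.1 and 2.2.2 say that neither protein product had yet been given to humans, and SAP Section 4.3.1 describes the study as first-in-human. The sponsor set a standard of less than 1% failure per year, yet its own inclusion criterion admits methods that are not on the list written for that standard.

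**Working it through.** No arithmetic applies beyond counting. The check sets the two lists side by side, follows one volunteer through both rules, and looks for text that ranks them.

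**Step 1. Compare the lists.**

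| Method | Criterion 8b and synopsis | Section 5.4.1.3 |
|---|---|---|
| Condom with spermicide | Named | Absent |
| Diaphragm with spermicide | Named | Absent |
| Cervical cap with spermicide | Named | Absent |
| Combined hormonal pill, patch or ring | Named | Listed, if ovulation is inhibited |
| Progestogen-only pill or injection | Named as pill or injection | Listed, if ovulation is inhibited |
| Progestogen implant | Only as another FDA-approved method | Listed, if ovulation is inhibited |
| Intrauterine device | Named | Listed |
| Intrauterine hormone-releasing system | Not named separately | Listed |
| Bilateral tubal occlusion | Tubal ligation is handled in 8a | Listed |
| Vasectomised partner | Named | Listed |
| Abstinence | Named | Listed |
| Any other FDA-approved method | Named, with no failure-rate condition | No such entry |

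Criterion 8b names three barrier methods. Section 5.4.1.3 has eight entries and none is a barrier method.

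**Step 2. Follow a barrier-only volunteer.** Under 8b, one named method suffices, so the criterion is met. Under 5.4.1.2, the method must be one described in 5.4.1.3, and a barrier method is not, so the condition is not met.

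**Step 3. Ask whether the 5.4.1.3 list is only illustrative.** It has no wording that introduces examples, and 5.4.1.2 asks for a method as described there. If the list were open, the 1% condition would still apply, and neither document says that a barrier method with spermicide meets it.

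**Step 4. Look for a ranking.**
- Section 5.3 directs screening to 5.3.1 and 5.3.2 and gives the principal investigator or a designee the last word. It does not say which list that decision follows.
- The closing sentence of 5.3.2 leaves the final evaluation to the investigator's medical judgment, which does not rank the lists either.
- Section 5.4.1 makes the contraceptive guidance mandatory, but does not say that it overrides 8b.
- Section 10.1.2 disallows waivers except for immediate safety concerns. It is therefore unclear whether enrolling a barrier-only user complies with the protocol or is a deviation.

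**Step 5. Take each way out.** If 8b governs, the site doses a volunteer whom 5.4.1.2 does not make eligible. If both rules apply and the stricter one binds, 8b and the synopsis tell screening staff that a method qualifies when it does not. On either reading, some text has to change.

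**The case against.** The strongest reply is that the rules can be read together. A volunteer must meet every inclusion criterion and must also follow the contraceptive guidance, so the stricter list binds and a barrier-only user is out. That reading is reasonable. It leaves the misdirection in 8b and the synopsis, which are where a site would screen from.

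The opposite reply is that the barrier list appears in three places (synopsis, 5.3.1 and 2.4.5). Section 5.4.1.1 also mentions premenarchal status in a trial of adults aged 18 to 55, which suggests that 5.4.1 is generic text and that 5.4.1.3 is the part to change. The conflict would remain until someone changed it. Resolving it by dropping the 1% standard would lower protection, a clinical trade-off for which the documents make no case.

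A third reply is that the safeguards are substantial, and this stands as a limit on the consequence:
- pregnancy testing at screening (2.4.5 and 8.1.4.4), at enrollment and on each vaccination day (criterion 9), and after a missed cycle (5.4.1.4)
- exclusion of anyone intending pregnancy (exclusion 8)
- counselling (5.3)
- no further vaccination after pregnancy, with follow-up to term (7.2 and 7.2.2)

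These measures detect pregnancy and stop further dosing. They do not prevent conception after a dose, and they do not settle which methods qualify.

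A reader might also infer that the rule in 5.4.1.1 for participants on hormone replacement is ambiguous, because it says that they "will be required to use one of the nonhormonal highly effective contraception methods if they wish to continue their HRT during the study". The documents do not support that. The sentence sits in the same subsection as 5.4.1.3 and uses its term, so it naturally refers to that list, which has nonhormonal entries to choose from.

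Finally, tubal ligation is treated differently across sections: no reproductive potential in 8a, a contraceptive method in 5.4.1.3. That is a separate tidying matter. Such a participant is eligible under either text.

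**Conclusion.** The inconsistency is real and concerns eligibility and participant safety. Three barrier methods satisfy 8b on their own, and none of the eight entries in 5.4.1.3 covers them.

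The conclusion rests on two assumptions: that the 5.4.1.3 list is complete as supplied, and that no ranking stands in material we do not have, such as the consent form or the manual of procedures.

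A reader might infer that 8b will lead to a certain number of extra pregnancies, or that barrier methods are shown to fail the 1% standard. The documents support neither inference, because they give no barrier failure rate and no count of barrier-only users. The conflict applies alike to all three arms and has no effect on sample size, power or analysis.

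**What to change.** Replace the method list in criterion 8b, the synopsis and Section 2.4.5 with a reference to Section 5.4.1.3. If the option of another FDA-approved contraceptive method is kept, limit it to one that meets the standard of less than 1% failure per year.

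The cost is a protocol amendment through the approvals in Section 10.1.1, with a matching change to the consent form if it repeats the barrier list. No procedure is added. Barrier-only users would need a listed method from at least 30 days before enrollment. That narrows recruitment, by an amount that the documents do not let us estimate.
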